ADVANCE EHR Data. We used electronic health record (EHR) data from the Accelerating Data Value Across a National Community Health Center Network (ADVANCE) clinical data research network (CDRN) data warehouse. The ADVANCE CDRN is a unique ‘community laboratory’ for research with underrepresented populations that includes patients receiving care in safety net clinics. The ADVANCE CDRN data warehouse includes *integrated* longitudinal EHR data from several organizations. Data from two ADVANCE partners, OCHIN and Health Choice Network (HCN), were used in the PACE study. From the ADVANCE CDRN, we included CHC members ‘live’ on their EHR as of January 1, 2013: 225 primary care CHCs in 10 states that expanded Medicaid as of 1/1/2014 (California, Hawaii, Maryland, Minnesota, New Mexico, Ohio, Oregon, Rhode Island, Washington, and Wisconsin) and 134 primary care CHCs in 6 non-expansion states (Florida, Kansas, Missouri, North Carolina, Texas, Montana). We included Wisconsin as an expansion state because although they did not expand Medicaid to 138% FPL they opened enrollment to adults with eligibility criteria of 100% FPL and therefore behaved more like an expansion state. Montana did not expand Medicaid until after our study period (expanded 1/1/2016), which included a one-year pre- (1/1/13-12/31/13) and a two-year post-period (1/1/2014-12/31/2015). Analyses included >4 million ambulatory visits among patients aged 19-64 (expansion states: 2.6 million visits from 499,719 patients; non-expansion states: 1.5 million visits from 370,600 patients).

Linkage between EHR and Medicaid administrative data. Oregon Medicaid administrative data was linked to OCHIN Oregon clinics in the ADVANCE CDRN to assess the receipt of healthcare services outside the Oregon CHCs and all healthcare expenditures.

Study Population and Study Period

The overall study population was adults ages 19-64 throughout the study period, 2012-2015. Included patients had ≥ 1 ambulatory visit at an eligible facility in the study period. Included facilities provided adult primary care and were ‘live’ on OCHIN’s or HCN’s EHR system by the start of the study period (1/1/2012). EHR data were extracted on all eligible patients, encounters, and facilities.

Overall, study analyses included >4 million ambulatory visits among patients aged 19-64 (expansion states: 2.6 million visits from 499,719 patients; non-expansion states: 1.5 million visits from 370,600 patients).

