Dependent Variables	Insurance coverage in EHR.
Covariates	NA
Analysis Plan	NA
Data Set Name	NA
Code Location	NA

The Impact of the Affordable Care Act Medicaid expansion on visit rates for a patient population with diabetes or pre-diabetes in safety net health centers

Full Citation	[name], N., R. Springer, M. Marino, H. Angier, M. Hoopes, H. Holderness and J. E. DeVoe. (2018) The Impact of the Affordable Care Act Medicaid expansion on visit rates for a patient population with diabetes or pre-diabetes in safety net health centers. J Am Board Fam Med. 31(6):905-916
Objective	To compare clinic-level uninsured, Medicaid-insured, and privately insured visit rates within and between expansion and non-expansion states prior to and after the ACA Medicaid expansion among the three cohorts of patient populations; and, to assess whether there was a change in clinic-level overall, primary care, preventive care visits, and diabetes screening rates in expansion versus non-expansion states from pre- to post-ACA Medicaid expansion.
Study Population	198 primary care community health centers: Non-pregnant patients aged 19-64 with ≥1 ambulatory visit between 01/01/2012-12/31/2015 (n=483,912 in expansion states; n=388,466 in non-expansion states).
Exclusion Criteria	Pregnant women
Independent Variables	Expansion status
Dependent Variables	1. Insurance coverage 2. Healthcare services
Covariates	Health insurance status, sociodemographic variables, urban/rural, state-level factors.
Analysis Plan	
 • Rate Ratios • Difference in Difference • GEE/Poisson models with sandwich variance estimators • Clustered models by CHC

	
 • Exchangeable covariance structure • Sensitivity analysis
Data Set Name	STATES, ELIGIBLE FACILITIES, ENCOUNTERS_AV1215_pipe, PAT_CONSORT_08312016, FAC_URBRUR
Code Location	BOX at OHSU

Prescription Opioid Use Patterns, Use Disorder Diagnoses, and Addiction Treatment Receipt after the 2014 Medicaid Expansion

Full Citation	Springer, R., M. Marino, S. Bailey, H. Angier, J. O’Malley, M. Hoopes, S. Lindner, J. DeVoe and N. [name]. Prescription Opioid Use Patterns, Use Disorder Diagnoses, and Addiction Treatment Receipt after the 2014 Medicaid Expansion. Resubmitted 12/18 to Addiction.

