Objective	To examine rates of opioid prescribing, Opioid Use Disorder (OUD) prevalence, and OUD treatment among Oregon Medicaid enrollees after the ACA Medicaid expansion; and to understand how insurance history and dose type are related to OUD diagnosis rates, as well as whether patients with OUD in the expansion population (of new enrollees and those ‘returning’ after coverage gaps) had different MAT participation rates than those previously continuously enrolled.
Study Population	Adults aged 19+64; continuously insured by Oregon Medicaid 1/2014-12/31/2015. N=225,295.
Exclusion Criteria	Patients with coverage gaps during study period; dual eligibles; hospice care; cancer diagnosis other than non-melanoma skin cancer.
Independent Variables	
 1. Insurance group 2. Episode type
Dependent Variables	
 1. Opioid filled prescription 2. Documented diagnosis of OUD 3. Chronic opioid use 4. Receipt of medication assisted treatment
Covariates	Age, sex, race, urban/rural, co-morbidities, zip code, federal poverty level, employment, and number of episodes
Analysis Plan	
 1. Inverse propensity weighting 2. Absolute standardized mean difference 3. Prevalences 4. Logistic regression 5. Cox proportional hazard 6. Multinomial logistic regression
Data Set Name	OUTPAT, OUTPATIENT_2015Q4, RX , RX_Q42015, SAMPLE_FLAGGED_FOR_EXPORT

	hospice_providers, mat_codes, opioid_ndcs_2016
Code Location	Box at OHSU

Following uninsured patients through Medicaid Expansion: healthcare utilization and diagnosed conditions

Full Citation	[name], N., S. Valenzuela, M. Marino, H. Angier, B. Hatch, M. Hoopes and J. E. DeVoe. Following uninsured patients through Medicaid Expansion: healthcare utilization and diagnosed conditions. Submitted Ann Fam Med 11/18.
Objective	Assess healthcare utilization and diagnosed health conditions among a cohort of community health center patients who were uninsured pre-ACA and follow them 24 months post-Affordable Care Act (ACA).
Study Population	All non-pregnant patients without insurance pre-ACA, aged 19-64 during the study period, with ≥ 1 ambulatory visit pre-ACA from 300 primary care CHCs 'live' on their EHR system as of 1/1/2012 in 11 states. N=138,246.
Exclusion Criteria	Pregnant women, insurance coverage prior to ACA.
Independent Variables	1. Insurance group
Dependent Variables	1. Healthcare utilization 2. Health conditions

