Exclusion Criteria	Non-smoking, pregnant, non-living, private insurance, Medicare insurance.
Independent Variables	Insurance Status
Dependent Variables	1. 'Quit' smoking status (yes/no) 2. Smoking cessation medication ordered (yes/no)
Covariates	Usual source of care after in follow up period.
Analysis Plan	1. Propensity score matching 2. Between group differences 3. GEE for clustering
Data Set Name	Smoking_model_set_PSmatches.sas7bdat
Code Location	OCHIN archive server

Observational Study of Racial/Ethnic Disparities in Health Insurance and Differences in Visit Type for a Population of Patients with Diabetes after Medicaid Expansion.

Full Citation	Angier, H., D. Ezekiel-Herrera, M. Marino, M. Hoopes, E. A. Jacobs, J. E. DeVoe and N. [name] (In press). Observational Study of Racial/Ethnic Disparities in Health Insurance and Differences in Visit Type for a Population of Patients with Diabetes after Medicaid Expansion. J Health Care Poor Underserved.
Objective	To understand the impact of the Affordable Care Act (ACA) Medicaid expansion on racial/ethnic health insurance disparities and differences in visit type for a population of patients with diabetes, by assessing changes pre- versus post-ACA in expansion compared with non-expansion states.
Study Population	Adults aged 19-64, diabetes diagnosis any time during study period, CHCs in ADVANCE network with EHRs live as of January 2013.
Exclusion Criteria	Pregnant women
Independent Variables	Expansion status
Dependent Variables	1. Health insurance status 2. Healthcare visit types a. Total b. Type
Covariates	Sex, age, FPL, Charlson comorbidity index score, state-level factors
Analysis Plan	1. Incidence rates 2. GEE Poisson models 3. Difference in Difference

Data Set Name	Analytic Data: PPDA Projects → PACE → Diabetes Disparities → Analytic Data Code: PPDA Projects → PACE → Diabetes Disparities → Code
Code Location	Box at OHSU

Assessing the prevalence of pre-existing conditions among community health center patients.

Full Citation	[name], N., H. Angier, M. J. Hoopes, M. Marino, J. [name], T. Schmidt and J. E. DeVoe. Assessing the prevalence of pre-existing conditions among community health center patients. Medical Care. Submitted 9/18
Objective	To assess the prevalence of pre-existing conditions pre- versus post-Affordable Care Act (ACA) for community health center (CHC) patients who gained insurance

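### In the diabetes disparities study, a diagnosis at any time in the study period gives entry to the cohort, so entry may depend on Medicaid expansion and the difference-in-differences may be biased

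*Combined protocol and SAP*

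**What the plan says.** In the Combined protocol and SAP, under Data Analyses, the table for the disparities study in patients with diabetes takes adults aged 19-64 with a "diabetes diagnosis any time during study period", seen at "CHCs in ADVANCE network with EHRs live as of January 2013". The aim is to measure the impact of expansion "by assessing changes pre- versus post-ACA in expansion compared with non-expansion states". The outcomes are health insurance status and visits, in total and by type. The methods listed are incidence rates, "GEE Poisson models" and DID. The covariates are "Sex, age, FPL, Charlson comorbidity index score, state-level factors". The table gives no study dates, no cut-off date for diagnosis, no rule for visits made before diagnosis, no unit or person-time definition, and no sensitivity analysis.

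Three other places bear on whether diagnosis can respond to expansion:

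- Hypothesis 1a, under Aim 1, predicts more visits in expansion states relative to non-expansion states.
- The companion study of visit rates in patients with diabetes or pre-diabetes sets out to assess "preventive care visits, and diabetes screening rates in expansion versus non-expansion states from pre- to post-ACA Medicaid expansion".
- The Decision Log (Table 4, entry of 04/25/16) records that blood glucose and HbA1c are both considered for the diagnosis of diabetes.

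The study that follows uninsured patients through expansion also treats diagnosis as an outcome ("Assess healthcare utilization and diagnosed health conditions among a cohort of community health center patients"). It requires a visit before the ACA for entry.

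**The concern.** A DID compares change over time in two groups whose membership should not itself be shaped by the exposure. Here a patient can enter through a diagnosis made in 2014 or 2015. If gaining coverage leads to more visits or more testing, some patients in expansion states are diagnosed, and so enter, because of expansion. A patient with the same undetected diabetes in a non-expansion state who is not tested stays out.

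Patients who enter this way are likely to have been uninsured or infrequent users before 2014, and covered or more frequent users afterwards. An excess of them on one side would look like an effect of expansion on coverage and visits among people with diabetes, even if nothing had changed for patients already known to have the disease. None of the listed covariates records when diagnosis occurred. If the excess also differed by race or ethnicity, the disparity contrast would be affected.

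**Working it through.** The table states no sample size, effect or power for this study, so there is no figure to reproduce. The check has three parts.

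**1. Share of the entry window that follows expansion.** The Combined protocol and SAP gives two study periods. Data Sources gives one year before (2013) and two years after (2014-2015). Study Population and Study Period gives 2012-2015.

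- 2012-2015: 24 / 48 = 50%.
- 2013-2015: 24 / 36 = 67%.

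The requirement that clinics be live by January 2013 suggests the second reading. These are shares of calendar time, not of patients; the documents do not give the share of patients.

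**2. Simple calculation with no true effect.** Assumed, not in the documents: 4.0 visits a year once diagnosed and 1.5 before. A fraction p of the cohort is first diagnosed after 1/1/2014, and a fraction f of those patients' post-period follows diagnosis. All visits of cohort members count in both periods.

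- Pre rate = (1 - p) x 4 + p x 1.5
- Post rate = (1 - p) x 4 + p x [f x 4 + (1 - f) x 1.5]
- DID ratio = (post/pre in expansion states) / (post/pre in non-expansion states)

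Non-expansion states, p = 0.20: pre = 3.50; post = 3.75 (f = 0.5) or 4.00 (f = 1). The ratios are 1.0714 and 1.1429.

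Expansion states, p = 0.24: pre = 3.40; post = 3.70 or 4.00. The ratios are 1.0882 and 1.1765. The DID ratio is 1.0882 / 1.0714 = 1.016, or 1.1765 / 1.1429 = 1.029.

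| p, expansion vs non-expansion | f = 0.5 | f = 1 |
|---|---|---|
| 22% vs 20% | 1.008 | 1.014 |
| 24% vs 20% | 1.016 | 1.029 |
| 30% vs 20% | 1.041 | 1.077 |

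The gap in p is simply assumed here, so a model that generates the gap is more informative.

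**3. Simulation of entry by detection.** There were 2,000,000 patients with diabetes per arm, followed for one year before and two years after expansion. All inputs are assumptions:

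- a gamma-distributed visit rate with mean 2 a year;
- 50% uninsured at baseline;
- coverage gained by 50% in expansion and 10% in non-expansion states;
- detection probability per visit of 0.1 or 0.3;
- visits raised by 0, 20 or 40% after gaining coverage;
- detection per visit multiplied by 1, 1.5 or 2 after gaining coverage.

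Truth is the DID ratio in all patients with diabetes, diagnosed or not. The table shows selected scenarios with detection probability 0.1.

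| Effect of gaining coverage | Outcome | Truth | Any-time cohort | Diagnosed before expansion |
|---|---|---|---|---|
| None on visits or detection | Total visits | 1.000 | 1.000 | 1.001 |
| None on visits or detection | Uninsured visits | 0.556 | 0.556 | 0.557 |
| Detection x 2 only | Total visits | 0.999 | 1.006 | 0.998 |
| Detection x 2 only | Uninsured visits | 0.555 | 0.515 | 0.551 |
| Visits +40%, detection x 2 | Total visits | 1.078 | 1.099 | 1.079 |
| Visits +40%, detection x 2 | Uninsured visits | 0.554 | 0.498 | 0.550 |

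The last scenario gives the largest departures of the any-time cohort: 1.099 / 1.078 = 1.019, about 2% on total visits, and 0.498 / 0.554 = 0.90, about 10% on uninsured visits. Across the scenarios in which gaining coverage changes visits or detection, total visits are overstated by under 0.5% to about 2%, and the fall in uninsured visits by about 0.5% to 10%. The share diagnosed only after expansion is higher in expansion states by up to 4 points (60.6% against 56.7%).

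The pre-expansion cohort stays within 0.002 of truth on total visits and within 0.004 on uninsured visits. The assumed effects of coverage do not depend on when a patient was diagnosed, so this shows that the restriction removes the selection. It does not show that the effect is the same in the narrower population.

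**The case against.** The strongest reply is that bias has not been shown. It needs expansion to change visits or detection differently in the two state groups. The plan expects the first only as a hypothesis, and the companion study only sets out to assess screening. If neither changes, the any-time cohort is unbiased, as the simulation confirms. This stands: a reader might infer that the DID is biased as a settled fact, and the documents do not support that.

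The table is also a summary of a paper listed as in press. The Decision Log (05/09/16) says that detailed documentation accompanies each dataset. A reader might infer that a patient diagnosed in 2015 has 2013 visits counted as diabetes visits. That is the natural reading, but the table does not state how visits or person-time are attributed.

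Size can be overstated too. Putting 35% against 20% with f = 1 into the simple formula gives (4.00 / 3.125) / (4.00 / 3.50) = 1.120. That needs a 15-point gap, against at most 4 points in the simulation, and every late diagnosis at the very start of 2014. Nothing in the documents supports either.

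The stated population is patients with diabetes, not patients already known to have it. If expansion brings undiagnosed patients into care, part of the resulting change is a policy effect. This also stands, and it is why the restriction changes the target population. It does not rescue the any-time cohort, which leaves out the undiagnosed patients in both state groups and may do so unequally.

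Finally, the plan contains related safeguards. The Decision Log (03/25/16) applies multilevel propensity weighting to all papers, and SAP section B.4.4 plans weighting for panel differences. The same section, on non-users in the post-period, recognises bias from defining patients by use that expansion causes. Its remedy models the probability of a visit. None of these deals with the date of diagnosis.

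**Conclusion.** The concern holds as a threat, not as a demonstrated bias. As written, the rule lets entry depend on an event that can follow expansion, over a window of which 50% to 67% lies after it. The plan itself supplies reasons to think that event may respond to expansion. The DID on insurance status and visits may be biased, most plausibly towards a larger coverage effect.

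The size cannot be computed from the documents. They give no detection rates, no share of patients diagnosed after 2013, no unit and no denominator. On the simulation's assumed inputs the distortion runs from under 1% to about 10%, with coverage more exposed than total visits. Any distortion of the racial and ethnic contrast is conditional on diagnosis gains differing by group, for which the documents give no figure. The point concerns one sub-study and does not touch the main analyses of the three aims.

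**What to change.** Run the DID in patients with a diabetes diagnosis recorded before 1/1/2014, with the same rule in both state groups. Make this the primary analysis or, at minimum, a prespecified sensitivity analysis beside the any-time cohort. Report the share first diagnosed after 1/1/2014 by state group and race/ethnicity, and limit the conclusion accordingly if the two cohorts differ. State the study dates in the same table, and how visits before diagnosis are counted.

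Counting person-time only from diagnosis is not a remedy. It still admits patients because of a post-expansion diagnosis, and they then contribute post-period visits with no pre-period counterpart.

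The work is one inclusion date and a re-run. The data agreement with OCHIN (Exhibit A, Time Period) already covers 1/1/2012 to 12/31/2017. The costs are some loss of precision and a target population narrowed to patients diagnosed before expansion. Because clinics need only be live by January 2013, some may offer only 2013 as a look-back year, so a first recorded diagnosis after 2013 will not always be a new one. The restricted cohort still selects on care received before 2014, but not on care that expansion could have changed.

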OCHIN and HCN	DUA	Allows OCHIN to share HCN data found in the ADVANCE CDM with OCHIN as a limited data set	6-3-16
OCHIN and OHSU	DUA	Adds Community Vital Signs data to original DUA	5-22-17
OCHIN and Oregon	DAA	Allows OCHIN to use state-owned Medicaid data	6-20-16

See Appendix 3 for full agreements.

Table 4. Decision Log

Study	Influence	Date of Decision	Decision Context	Decision
PACE	Insurance Validation Paper ([name])	03/29/16	PPD Meeting	Will exclude Medicare/Medicaid dual eligibles (since we cannot determine who they are in the ADVANCE data).
PACE	Insurance Validation Paper ([name])	03/29/16	PPD Meeting	Will exclude visits coded as being paid by another public payor – these don't provide information about Medicaid coverage.
PACE	Data Methods	01/12/16	PPD Meeting	Data Pull will include all states, however down the road if there are complications based on a state's data they will be excluded.
PACE	Bio Marker Paper ([name])	02/23/16	PPD Meeting	Analysts will use Oregon Medicaid administrative data to create insurance cohorts to validate ADVANCE visit based insurance groups.
PPD	Definitions	03/15/16	PPD Meeting	Patient state and clinic state will be given, classified as expansion vs non expansion. Patient state will be state at the patient's most recent encounter, not historical state at date of encounter.
PPD	Data Methods	03/25/16	Journal Club	Currently, the methods used within the "Propensity score weighting with multilevel data" article by Li, Zaslavsky and Landrum will be applied to all papers.
PPD	Data Methods	04/01/16	[name]/ [name]/ [name]	Base data pull: Clinic inclusion criteria OCHIN: dept type=primary care, public health, or medical specialty specified as internal med, peds, or women's health. School-based health centers (SBHCs) included. Health Choice network: site type=CHC, peds, SBHC, or hospital specified as outpatient clinic. Exclude based on facility names including radiology, mental, behavioral, substance, dental, pharmacy, or lab. Facility type categorized into: primary care, public health, pediatrics, women's health, mobile, specialty, and SBHC.

PPD	Data Methods	04/01/16	[name]/ [name]/ [name]	Base data pull: the following algorithm was used to assign go-live dates to HCN facilities: - PM golive = earliest encounter date per facility that is >=1/1/2003 (earliest actual go-live date for an HCN facility is in 2003) - Identify earliest vitals date that is >=1/1/2003 --> if earliest vitals date is >= PM golive date then EHR golive=earliest vitals date; else if earliest vitals date < PM golive then EHR golive=PM golive; else if no vitals date, then EHR golive = null.
PPDA	Data Methods	04/25/16	Analyst Meeting	Blood glucose and HbA1c both in consideration for diagnosis of diabetes (included in Nichols algorithm).
PPDA	Data Methods	05/02/16	Email	'Encounters' in the OCHIN system can include non-face-to-face contacts such as telephone visits, mychart updates, etc. In past studies, we have typically considered 'visits' to be the face-to-face and in-clinic subset of 'Encounters', though this definition has varied across studies/analyses. At times 'encounter' and 'visit' has been used interchangeably.
PPDA	Data Methods	05/02/16	Email	Other Ambulatory Visit (OA): Includes other non-overnight ambulatory encounters such as dental visits, hospice visits, home health visits, skilled nursing visits, other non-hospital visits, as well as telemedicine, telephone and email consultations. May also include "lab only" visits (when a lab is ordered outside of a patient visit), "pharmacy only" (e.g., when a patient has a refill ordered without a face-to-face visit), "imaging only", etc.
PPDA	Data Methods	05/02/16	Email	Ambulatory Visit (AV): Includes visits at outpatient clinics, physician offices, same day/ambulatory surgery centers, urgent care facilities, and other same-day ambulatory hospital encounters, but excludes emergency department encounters. Not limited to medical visits (e.g., includes mental/behavioral health visits).
PPDA	Data Methods	05/02/16	Email	If additional encounter details, such as provider type, facility type, level of service, etc., are used in the inclusion/exclusion criteria, they should be clearly specified in the outlines (i.e. "OB qualifying encounter types": face-to-face with x diagnoses, y procedures, provider type(s), etc.).

PPDA	Data Document ation	05/09/16	Analyst Meeting	High-level patient inclusion/exclusion criteria for each paper will be tracked in columns in Manuscript Tracker; more detailed documentation (e.g., 'readme' and data dictionaries) will be provided with each study dataset and included as an attachment in the manuscript tracker.
PPDA	Data inclusion	06/06/16	Analyst Meeting	Residents of states that are not included in study (but were seen at eligible facilities in one of our 19 states) will be excluded.
PPDA	Data Methods	06/13/16	Analyst Meeting	There may be data errors in the provider_type variable in the encounters file (i.e., an AV visit may have dentist listed as provider type – which one is correct?) – safer to use AV count based on ADVANCE data team’s large amount of work on this categorization.
PPDA	Data Definition		Email	PACE: Pre=2013, Post=2017/PREVENTD: Pre=2012, Post=2020
PPDA	Data inclusion	06/16/16	Manuscript Meeting	Keep continually insured, uninsured in pre and mix of all insured visits, track how many visits were paid by Medicaid (will be able to isolate based on persons insurance status), throw out public insurance/Medicare patients. Patient with continual private insurance in periods will be continuously insured.
PPDA	Data inclusion	06/16/16	Manuscript Meeting	Biomarker change could change based on preexisting condition in Medicare group, Patients with Medicare record will be excluded (all papers).
PPDA	Data analysis	8/18/16	Manuscript Meeting	Include WI as an expansion state in all analyses.
PPDA	Data Methods	06/14/17	Manuscript meeting	HCN data for "smoking" not specific enough; using tobacco-only analysis instead of separating out type of Tobacco use (unless able to code further).
PPDA	Data Methods	06/14/17	Manuscript meeting	Collect pre-AND post- Charlson Comorbidity Index score (using problem list)
PPDA	Data analysis	1/4/18	PPDA Manuscript Meeting	ADVANCE data from 2017 to be pulled February 2018.
PPDA	Data analysis	2/14/18	Other	Refer to as “Enhanced Charlson Comorbidity Index” and cite: Charlson ME, Charlson RE, Marinopoulos SS, Briggs WM, Hollenberg JP. The Charlson Comorbidity Index is adapted to predict costs of chronic disease in primary care patients. J Clin Epidemiol. 2008; 61:1234-40.

Research Integrity Office

IRB MEMO

[name]
[name]
[name] [contact]

